6.9 LIVER ADVERSE EVENTS

The following algorithm will be used to monitor for drug-induced liver injury (DILI):

If isolated transaminase (AST or ALT) elevations are observed, defined as: Normal bilirubin and absence of clinical hepatitis, AND

- 1. ALT or AST \geq 5 times the ULN if normal at baseline, OR
- 2. ALT or AST \geq 3 times the baseline or \geq 400 U/L if abnormal at baseline

Then

- 1. Repeat liver profile (ALT, AST, bilirubin and PT/INR) within 2 to 3 days, AND
- 2. Monitor the patient with laboratory testing and physical examination 2 to 3 times per week as per the "close observation" definition in the DILI guidance (https://www.fda.gov/downloads/Drugs/.../Guidances/UCM174090.pdf).

If any ONE of the following criteria is met:

- Transaminases (ALT or AST \geq 3 x baseline) AND bilirubin (total bilruibin \geq 2 x ULN), OR
- Cholestatic markers (ALP or GGT > 2 x baseline), OR
- Isolated ALT/AST ≥ 8x ULN or 600 U/L in the presence of normal CPK and LDH and not secondary to cholangitis, OR
- INR increase > 1.5 refractory to vitamin K administration

OR: if any ONE of the following criteria is met for total bilirubin unrelated to hemolysis:

- 1. Doubling of total bilirubin
 - OR: any increase in total bilirubin if there are symptoms of clinical hepatitis (e.g., vomiting, nausea, right upper quadrant pain),
 - OR: there are immunological reactions (rash or >5% eosinophilia),

Then

- 1. study medication must be interrupted, and
- 2. a drug-induced liver injury workup must be initiated for alternate etiologies;
- 3. repeat a liver profile (ALT, AST, total bilirubin, direct bilirubin, ALP) and PT/INR within 48 to 72 hours;
- 4. monitor the patient with further laboratory testing and physical examination 2 to 3 times per week as per the "close observation" definition in the DILI guidance (https://www.fda.gov/downloads/Drugs/.../Guidances/UCM174090.pdf.
- 5. If a subject lives in a remote area, they can be tested locally and the results communicated to the investigator promptly.

Rechallenge

- 1. Only if a firm alternate etiology is identified AND liver tests have returned to baseline (a rechallenge may be considered)
- 2. If cholangitis is the etiology diagnosis must be firmly established according to the protocol definition before a rechallenge is considered

Rechallenge is not recommended if it is determined that the subject has had a drug induced liver injury.

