3.2.2 Exclusion Criteria

To be eligible for entry into the study, the subject must not meet any of the exclusion criteria listed below:

- Presence of documented secondary sclerosing cholangitis (such as ischemic cholangitis, recurrent pancreatitis, intraductal stone disease, severe bacterial cholangitis, surgical or blunt abdominal trauma, recurrent pyogenic cholangitis, choledocholithiasis, toxic sclerosing cholangitis due to chemical agents, or any other cause of secondary sclerosing cholangitis) on prior clinical investigations;
- 2. Small duct PSC;
- 3. Presence of percutaneous drain or bile duct stent;
- 4. History of cholangiocarcinoma or clinical suspicion of new dominant stricture within 1 year by MRCP/ERCP or clinical judgement. Presence of dominant stricture without ERCP evidence of cholangiocarcinoma is acceptable if stable for ≥ 1 year.;
- 5. Ascending cholangitis within 60 days prior to Screening;
- 6. Concomitant overlap syndrome with autoimmune hepatitis (AIH) as diagnosed by AST or ALT > 5x ULN, AND
 - i. positive smooth muscle antibody and/or liver-kidney microsomal antibody (LKM), or
 - ii. IgG >ULN, or
 - iii. Biopsy suggestive for AIH

- 7. Concomitant overlap syndrome with primary biliary cholangitis (PBC) as diagnosed by either:
 - i. positive AMA or
 - ii. biopsy suggestive for PBC
- 8. History of alcohol or substance abuse or dependence;
- 9. Prior or planned liver transplantation;
- 10. Presence of alternative causes of chronic liver disease, including alcoholic liver disease, nonalcoholic steatohepatitis, primary biliary cirrhosis, autoimmune hepatitis;
- 11. Platelet count below 125,000/mm³, albumin below 3.0 g/dL, International Normalized Ratio (INR) > 1.2, or a history of ascites, or encephalopathy, or history of esophageal variceal bleeding;
- 12. Anticoagulant therapy, with the exception of acetylsalicylic acid;
- 13. Severe active IBD or flare in colitis activity within the last 90 days requiring intensification of therapy beyond baseline treatment;
- 14. Use of oral prednisone/prednisolone > 10 mg/day;
- 15. Hospitalization for colitis within 90 days;
- 16. AST > 5 x ULN;
- 17. ALT > 5 x ULN;
- 18. Total bilirubin > 1.2 x ULN. If total bilirubin result at screening is > ULN but \leq 1.2 x ULN, a confirmatory total bilirubin should be collected after 21 days. If the confirmatory total bilirubin remains \leq 1.2 x ULN, and all other eligibility criteria continue to be met, the subject will be eligible.;

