For subjects participating in the PK substudy, additional blood samples for PK analysis will be collected, processed, and sent to the designated central laboratory. PK samples will be collected at the following timepoints (see Table 1PK):

- Pre-dose
- 1, 2, 3, 4, 6, and 8 hours post-dose

Subjects participating in the PK substudy will be required to maintain a dosing diary. The date and time of each dose of study medication taken on the last 3 days prior to the Week 6 visit must be recorded, and the diary must be brought back to the site at the Week 6 clinic visit.

Following the successful completion of all Baseline procedures, the subject will self-administer the first dose of the study medication, consisting of 4 tablets, under the supervision of study personnel. The subject will be provided an entire 6-week supply of study medication consisting of a total of 90 dosage units, each containing 4 tables. The subject will be instructed to swallow the contents of one dosage unit containing 4 tablets in the morning, and one dosage unit containing 4 tablets in the evening, each day until they return to the investigational site 6 weeks later for the next visit. Subjects will be instructed to contact the investigational site immediately if any problems or concerns arise.

5.1.3 Double-Blind Treatment Period - Weeks 2, 4, and 6

During the double-blind treatment period, the following procedures and assessments will be conducted on Weeks 2 and 4:

- Subjects are required to provide blood samples for CBC, CMP, and Lipids. This will not require a visit to the study site and will involve local sample collection.
- Subjects will be contacted by the Investigator, or one of their staff, to discuss the occurrence of any AEs, any new or changes in concomitant medications, adherence to the treatment schedule, and compliance with the requirement to visit a pre-specified clinical laboratory for CBC, CMP, and Lipids. Any new medications that are being taken are, by default, to be considered as being necessitated by an AE. If necessary, subjects may be asked to visit the investigational site, at the Investigator's discretion.

• It is recognized that some investigational sites may require subjects to come to the clinic for these visits and related activities.

During the double-blind treatment period, the following procedures and assessments will be conducted during the visit to the investigational site on Weeks 6:

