5.1.7 Follow-up Period (Week 22)

Subjects will undergo follow-up evaluations 4 weeks after the last dose of study drug. The follow-up can be via phone, providing the patient has no health concerns related to the study. The subject may be asked to return to the investigational site if the Investigator thinks it is advisable for safety reasons. The following assessments will be conducted by phone or other contact at Week 22:

- AE monitoring
- Concomitant medications (query for any possible relationship to an AE)

Following the completion of the follow-up procedures, the subject is officially discharged from the study.

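### Protocol Section 6.9 requires less liver follow-up for the same ALT/AST rise when bilirubin is moderately raised than when it is normal

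*Protocol*

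**What the plan says.** Section 6.9 of the protocol has two tiers.

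**Monitoring tier.** It applies when "isolated transaminase (AST or ALT) elevations are observed, defined as: Normal bilirubin and absence of clinical hepatitis", and ALT or AST is at least 5 x ULN (normal baseline), or at least 3 x baseline or 400 U/L (abnormal baseline). The first action reads "Repeat liver profile (ALT, AST, bilirubin and PT/INR) within 2 to 3 days, AND" and the second is laboratory testing and examination 2 to 3 times a week.

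**Interruption tier.** Drug is interrupted, a work-up is started, the profile is repeated in 48 to 72 hours and close observation follows if any one of these is met:
- ALT/AST at least 3 x baseline with total bilirubin at least 2 x ULN;
- ALP or GGT above 2 x baseline;
- ALT/AST, again called isolated, at least "8x ULN or 600 U/L in the presence of normal CPK and LDH", and not due to cholangitis;
- INR above 1.5 despite vitamin K;
- for bilirubin not explained by hemolysis: "Doubling of total bilirubin"; or "any increase in total bilirubin if there are symptoms of clinical hepatitis"; or rash or eosinophilia.

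**Entry and schedule.** Exclusion 18 (Section 3.2.2) admits bilirubin up to 1.2 x ULN; for a value above ULN, "a confirmatory total bilirubin should be collected after 21 days". Between clinic visits (Sections 5.1.3 to 5.1.5), "Subjects are required to provide blood samples for CBC, CMP, and Lipids" every two weeks. Table 1 schedules no chemistry after Week 18, and for Week 22, "The follow-up can be via phone, providing the patient has no health concerns related to the study" (Section 5.1.7).

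**The concern.** The two tiers do not meet. Normal bilirubin is a condition for monitoring, but interruption needs a bilirubin well above normal unless another trigger is present. Between the two, a higher bilirubin removes a safeguard: the same ALT/AST gets a timed repeat with normal bilirubin and none with a moderately raised one. What is at stake is how soon a possible drug-induced liver injury is rechecked while dosing continues.

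Two features add to this. A subject admitted under exclusion 18 with bilirubin above ULN cannot enter the monitoring tier at any ALT/AST while it stays there. And the interruption bullet reuses the word *isolated*, which the section defines only once, as normal bilirubin without clinical hepatitis. If that definition carries over, the ALT/AST-only stop also lapses when bilirubin is raised.

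**Working it through.** The plan gives no figure to reproduce, so the check is to write Section 6.9 as a decision table and run cases through both tiers.

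**Assumptions.** Doubling of bilirubin is measured from baseline (the text gives no reference). ALT ULN is not stated; 40 U/L is used, with 30 and 50 as a range. Unless a row says otherwise, the subject has no hepatitis symptoms, rash, eosinophilia, ALP/GGT or INR trigger, has normal CPK and LDH, and has no cholangitis.

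**Cases** (all values x ULN)

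| Baseline ALT | ALT now | Bilirubin, baseline to now | Monitoring | Interruption |
|---|---|---|---|---|
| 1.0 | 7 | 0.9 to 1.0 | yes | no |
| 1.0 | 7 | 0.9 to 1.5 | no | no |
| 0.8 | 6 | 0.8 to 1.3 | no | no |
| 0.8 | 6 | 0.8 to 1.3, with nausea or rash | no | yes |
| 0.8 | 6 | 0.5 to 1.05 (doubled) | no | yes |
| 2.0 | 6.5 | 0.9 to 1.0 | yes | no |
| 2.0 | 6.5 | 1.15 to 1.15 | no | no |
| 2.0 | 6.5 | 1.15 to 1.95 | no | no |
| 2.0 | 9 | 0.9 to 1.5 | no | depends on reading |

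The first two rows hold on every reading: 7 is above 5 and below 8 x ULN; 7 x 40 = 280 U/L (210 to 350 for ULN 30 to 50), below 600; 1.5 is below 2 x ULN; and 1.5 / 0.9 = 1.67 is not a doubling.

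**Bilirubin width of the gap.** For ALT/AST at least 3 x baseline, it runs from above 1.0 to below min(2.0, 2 x baseline bilirubin), in x ULN:
- baseline 0.5 or less: none (2 x 0.5 = 1.0)
- baseline 0.6: above 1.0 to below 1.2
- baseline 0.8: above 1.0 to below 1.6
- baseline 0.9: above 1.0 to below 1.8
- baseline 1.0 to 1.2: above 1.0 to below 2.0

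**ALT/AST width of the gap.**
- Normal baseline: 5 to below 8 x ULN, which is 200 to below 320 U/L at ULN 40 (150 to below 240 at 30; 250 to below 400 at 50).
- Abnormal baseline, if 8 x ULN stops everyone: 3 x baseline to below 8 x ULN. Baseline 1.5 gives 4.5 to below 8; 2.0 gives 6 to below 8; 2.5 gives 7.5 to below 8; none from 8 / 3 = 2.67 x ULN upward for ULN 30 to 50.
- Abnormal baseline, if 600 U/L is the stop meant for them: the lower of 3 x baseline and 400 U/L, up to below 600 U/L. At ULN 40, baseline 2 x ULN gives 240 to below 600; baseline 4 x ULN gives 400 to below 600.
- If *isolated* means normal bilirubin: same lower limits, no upper limit.

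**Timing.** Chemistry is drawn every 14 days, so the next required profile can be 14 - 3 = 11 to 14 - 2 = 12 days later than under the monitoring tier. The checks forgone over that interval number 2 x 2 = 4 to 3 x 2 = 6. On the strict reading of *isolated*, ALT of 8 x ULN or more in this bilirubin range could continue for 14 x 2 = 28 doses before the next required profile.

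**Smaller gap.** A subject at the ALT/AST limit with hepatitis symptoms but no bilirubin increase is excluded from monitoring by the symptoms and does not meet the symptom stop, which needs an increase.

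**The case against.** The strongest reply is that the gap is narrow and other provisions stand behind it. One ALP/GGT, INR, symptom-with-bilirubin-increase, rash or eosinophilia trigger brings full interruption. Laboratory findings showing clinical deterioration at Weeks 6, 12 and 18 are recorded as adverse events; clinically significant ones are followed until resolution (Section 6.1), and follow-up is to be proactive (6.8). Staff contact subjects at the intermediate weeks and may call them in. Section 7.1 allows discontinuation on judgement and requires it for a dominant stricture or a second cholangitis episode. Section 7.4 has trial stopping rules, and the SAP (Sections 1.1 and 3.4) adds a DSMB. All of this is correct and limits the residual risk, but none of it sets a timed repeat or an interruption on ALT/AST values.

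Four narrower objections stand in part.
- Exclusion 18 supplies only the bilirubin condition from Day 1; exclusions 16 and 17 bar ALT/AST above 5 x ULN, so in practice an on-study rise is still needed.
- The 11 to 12 days is a ceiling: the 2 to 3 days run from when the elevation is observed, so laboratory turnaround shortens the difference.
- After Week 18 scheduled dosing has ended, so only the timed recheck is at stake, and the phone contact is conditional.
- *Isolated* in the interruption bullet can be read as meaning without the combined criterion. The unlimited range and the 28 doses therefore depend on one reading and do not carry the conclusion.

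It can also be said that the remedy only equalises monitoring rather than making it stricter at higher bilirubin. That is deliberate: where interruption should begin is a clinical choice, and the limits are left alone.

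**Conclusion.** The concern holds, with high confidence. On the text of Section 6.9, an ALT/AST rise that requires a 2 to 3 day repeat and close observation with normal bilirubin requires neither when bilirubin is above ULN, below 2 x ULN and not doubled, and no other trigger is met. For a normal baseline the range is at least 5 to below 8 x ULN, and the next required profile may come up to 11 to 12 days later.

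The bilirubin ranges assume doubling is from baseline; the U/L figures assume a ULN of 30 to 50. The upper ALT/AST limit depends on the meaning of *isolated*, which the text leaves open. The documents do not show how many subjects would enter the gap. The point should be corrected as a matter of subject safety.

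**What to change.** Make two wording changes in Section 6.9.

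1. Monitoring tier: delete the word *isolated*, and replace the bilirubin and clinical-hepatitis condition with *no interruption criterion below is met*. The ALT/AST limits stay. Every subject at a limit is then either monitored or interrupted, which also closes the smaller gap, by monitoring.
2. ALT/AST-only stop: replace *isolated* with *at any bilirubin*, keeping the 8 x ULN / 600 U/L limits and the CPK/LDH and cholangitis conditions.

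Leave all other triggers and limits unchanged. With the revised text run under each reading of the 8 x ULN / 600 U/L bullet, with and without symptoms and with CPK/LDH normal or not, every tested combination at the monitoring limit required monitoring or interruption, and none got less than under the current text.

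The cost is a safety amendment to one section, extra repeat profiles and checks 2 to 3 times a week for subjects already at an ALT/AST limit, and some extra interruptions at or above 8 x ULN / 600 U/L where sites now read *isolated* as normal bilirubin.

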6.10 PREGNANCY

When any member of the study staff becomes aware of a subject's (or subject's partner's) pregnancy, the site staff must report the pregnancy to the medical monitor and the within 24 hours by using the Pregnancy Notification Form. The female subject will discontinue study medication. The pregnancy will be followed until there is an outcome and the outcome is reported to the sponsor.

7.0 STUDY OR SITE TERMINATION AND SUBJECT DISCONTINUATION

7.1 ADVERSE EVENT STOPPING RULES

If a subject experiences an AE that, in the judgment of the investigator, the sponsor, or the medical monitor, presents an unacceptable consequence or risk to the subject, the subject may be discontinued from the study.

If a participant develops cholangitis or an inflammatory bowel disease (IBD) flare twice during the trial, then the patient should be discontinued from study drug, but maintained in the study for safety follow-up.

- Cholangitis is defined as cholestasis and systemic inflammation demonstrated by clinical signs or blood test results in addition to biliary manifestations demonstrated by imaging.
- Inflammatory bowel disease flare-ups are defined as unexpectedly frequent and/or urgent bowel movements, diarrhea, bloody stools or abdominal pain, not requiring systemic immunosupression with a corticosteroid or a biological agent.

If a participant develops a dominant stricture or an IBD flare requiring new or increased of immunosupressive therapy (systemic corticosteroids or biologics), then the patient should be discontinued from study drug, but maintained in the study for safety follow-up.

• A dominant stricture is defined as intervention due to symptoms, compelling imaging results, or a prominent increase in liver biochemical markers.

7.2 NONCOMPLIANCE

After the investigator, the medical monitor, or study monitor consult (and the sponsor if appropriate), a subject may be discontinued from the study for the following administrative reasons:

- Failure to receive study medication or treatment as mandated by the instructions provided in Section 4.0
- Failure to comply with protocol requirements
- Unauthorized, subject-initiated changes in dosing regimen

7.3 WITHDRAWAL OF CONSENT

Any subject who withdraws consent for any reason at any time during the study will be discontinued from the study, and the reason(s) will be documented on the appropriate eCRF page. Subjects will be encouraged to complete the study; however, they may voluntarily withdraw at any time. The investigator will provide a written explanation of the reason for discontinuation in a source document and this information will be recorded on the appropriate eCRF page. Subjects will be specifically queried to determine whether or not withdrawal of consent might have been due to an adverse event. If a subject withdraws before completion, every effort should be made to complete the assessments scheduled during the follow-up period [termination/end of study visit]. A subject may be removed from the study for the reasons described in Section 7.1 through Section 7.3.

7.4 PREMATURE STUDY OR SITE TERMINATION

If the sponsor, investigator, medical monitor, study monitor, or appropriate regulatory officials discover conditions arising during the study that indicate that the study should be halted or that the site should be terminated, this action may be taken after appropriate consultation among the sponsor, investigator, medical monitor, and study monitor. The Common Terminology Criteria for Adverse Events (CTCAE) will be used to for the assessment of trial stopping criteria.

The study trial will be stopped if:

- Three patients develop the same Grade 3 CTCAE
- OR: Two patients develop any Grade 4 CTCAE
- OR: One patient develops a Grade 5 CTCAE

Additional conditions that may warrant termination of the study include, but are not limited to, the following:

- The discovery of an unexpected, serious, or unacceptable risk to the subjects enrolled in the study
- A decision on the part of the sponsor to suspend or discontinue testing, evaluation, or development of the product

A study conducted at a single site in a multicenter study may also warrant termination under the following conditions:

- Failure of the investigator to enroll subjects into the study at an acceptable rate
- Failure of the investigator to comply with pertinent regulations of appropriate regulatory authorities
- Submission of knowingly false information from the site to the sponsor, study monitor, or appropriate regulatory authority
- Insufficient adherence to protocol requirements

Study termination and follow-up will comply with the conditions set forth in International Council for Harmonisation E6, Guideline for Good Clinical Practice, Sections 4.12, 4.13, 5.20, and 5.21.

8.0 DATA COLLECTION AND PROCESSING AND STATISTICAL ANALYSIS

8.1 DATA COLLECTION AND PROCESSING

Electronic case report forms (eCRFs) will be used to capture study assessments and data. The study coordinator or other delegated study staff will enter data from source documents into the eCRFs. All eCRFs will be reviewed and source-verified by the study monitor during periodic site visits, and the study monitor will ensure that all data in the eCRF are correct and complete. Before or between visits, the medical monitor or study monitor may conduct a preliminary medical review of the eCRFs. Once the eCRFs are completed and source-verified, the investigator must electronically sign all required eCRF pages, verifying the accuracy of all data contained in the eCRFs.

Training will be provided for the electronic data capture (EDC) system. All study staff using the EDC system must have the necessary education, training, and experience or any combination of these. The investigator will be responsible for documenting employee education, training, and previous experience that pertain to the EDC system for all site staff using the EDC system.

The investigator must maintain adequate security of the EDC system, including documentation that all users have been trained on the appropriate standard operating procedure and a list of authorized users. To ensure all data entries can be tracked, all personnel responsible for data entry must obtain a unique user identification (user ID) and password before any data can be entered in the eCRFs. Authorized study staff will be assigned a unique user ID only after receiving standard operating procedure training.

If electronic data systems other than those provided and maintained by the sponsor are used for documentation and data capture, the investigator must ensure that the systems are validated and that data are backed up as described in Section 9.2.

8.2 STATISTICAL ANALYSIS

8.2.1 General Overview

The data will be summarized in tables by treatment period and treatment group, as appropriate, showing the number of subjects with nonmissing data (n), mean, standard deviation, median, minimum, and maximum for continuous data and showing counts and percentage for categorical data. Data will also be listed as deemed appropriate. All statistical analyses will be performed and data appendices will be created by using SAS version 9.4 or later.

All statistical tests will be two-sided with an alpha (α) level of 0.05.

